4.3 Concomitant Medications

Anticoagulation therapy with enoxaparin sodium (1 mg/kg twice a day) will be initiated at least 48 hours prior to initiation of study treatment. Subjects not currently anticoagulated with enoxaparin will be transitioned to enoxaparin. Transition to enoxaparin should occur when the next dose of anticoagulant is due i.e. there shall be no overlap in anticoagulant dosing. When the subject is due for their next dose of anticoagulant, enoxaparin should be started at 1 mg/kg twice daily. When the subject has been solely on enoxaparin for at least 48 hours, the study treatment may be performed.

Following conclusion of treatment, the subject should remain on enoxaparin 1 mg/kg bid for 90 days. The subject may then be transitioned to long term anti-coagulation at the Investigator's discretion. If necessary, enoxaparin may be converted to an oral anticoagulant after 30 days (e.g. 20 mg rivaroxaban daily).

4.4 Prohibited Medications

The use of platelet glycoprotein IIb/IIIa receptor antagonists (abciximab, tirofiban, eptifibatid) and oral thienopyridine anti-platelet drugs during or within 24 hours of the completion of study treatment is not permitted. The use of aspirin and non-steroidal anti-inflammatory drugs is discouraged while subjects are receiving anticoagulant therapy unless there is a compelling indication.

4.5 Subject Withdrawal

Subjects may withdraw from participation at any time during the clinical study. All data collected prior to withdrawal shall remain part of the study. Every effort shall be made to encourage the subject to remain in the trial. If the subject declines, determine and document the reason for withdrawal.

4.6 Revascularization

If, at any time during the follow-up period a subject is found to have re-occlusion of a venous segment that is associated with escalation of symptoms, the subject may undergo revascularization using any method the treating physician feels is appropriate. The subject shall remain in the study and shall attend all planned follow-up visits. All revascularization procedures shall be documented on the revascularization case report form.

5.0 SAFETY REPORTING

5.1 Adverse events

An adverse event (AE) is defined as any untoward medical occurrence associated with the use of an investigational intervention in humans, whether or not considered intervention related. An AE can be any unfavorable and unintended sign, symptom, or disease temporally associated with the use of an intervention and does not imply any judgment about causality. An AE can arise with any use of the intervention.

5.2 Suspected Adverse Reaction

Suspected adverse reaction (SAR) means any AE for which there is a reasonable possibility that the intervention caused the AE. For the purpose of reporting, 'reasonable possibility' means there is evidence to suggest a causal relationship between the intervention and the AE. A SAR implies a lesser degree of certainty about causality than adverse reaction. An adverse reaction means any AE caused by an intervention. Adverse reactions (ARs) are a subset of all SARs where there is reason to conclude that the intervention caused the event.

5.3 Serious

An AE is considered "serious" if, in the view of either the investigator or sponsor, it results in any of the following outcomes:

1. Death
2. Life-threatening (had the event occurred in a more severe form, might have caused death)
3. Inpatient hospitalization or prolongation of existing hospitalization
4. Permanent impairment of a body structure or body function; a persistent or significant incapacity or substantial disruption of the ability to conduct normal life functions (for example, persistent or significant loss of function, disability, or incapacity)
5. Congenital abnormality or birth defect if subject should become pregnant within 90 days of the treatment completion
6. Important medical events that may not result in death, be life-threatening, or require hospitalization may be considered serious when, based upon appropriate medical judgment, they may jeopardize the subject and may require medical or surgical intervention or prevent one of the outcomes listed in this definition.

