5.9 Adverse events related to alteplase and definition of major bleeding

AEs related to alteplase are well-described and consist mainly of bleeding complications, including major and intracranial hemorrhage. The incidence of these complications has been quantified in subjects receiving comparatively large systemic doses of alteplase for acute myocardial infarction, stroke, and acute pulmonary embolism. Any bleeding that is attributable to alteplase is most likely to occur within 24 hours of treatment and is very unlikely to occur after 72 hours. Therefore, all bleeding events that occur within 72 hours of ultrasound-accelerated catheter-directed fibrinolysis will be attributed to the use of alteplase.

The following definition of major bleeding¹² (ISTH) shall be used: As general principles, a definition of major bleeding needs to be based on objective criteria, and major bleeds are those that result in death, are life-threatening, cause chronic sequelae or consume major health-care resources. With this in mind, the Control of Anticoagulation Subcommittee recommends the following criteria for major bleeding in non-surgical subjects:

1. Fatal bleeding, and/or
2. Symptomatic bleeding in a critical area or organ, such as intracranial, intraspinal, intraocular, retroperitoneal, intra-articular or pericardial, or intramuscular with compartment syndrome, and/or
3. Bleeding causing a fall in hemoglobin level of 20 gL⁻¹ (1.24 mmol L⁻¹) or more, or leading to transfusion of two or more units of whole blood or red cells

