5.12 Categorization of adverse events

All AEs must be classified according to intensity or severity, relatedness, outcome, and treatment or action taken.

Intensity or severity

The following categories for intensity or severity of an AE should be used in reporting:

Mild	Awareness of a symptom or sign that does not interfere with the subject's usual activity or is transient and resolves without treatment and without sequelae
Moderate	Interferes with the subject's usual daily activities, but he or she is still able to function
Severe	Interrupts a subject's usual daily activities and generally requires medication, surgery, or other intervention for treatment

Relatedness

Each AE should be evaluated as to whether it was related to the study procedures, thrombolytic and anticoagulation drugs, or EkoSonic® Endovascular System as follows:

Definite	An AE that has a causal relationship to the drug (recombinant t-PA), anticoagulation medication, or the EkoSonic® Endovascular System
Probable	An AE that has a 'reasonable possibility' of a causal relationship to the use of recombinant t-PA, anticoagulation medication, or the EkoSonic® Endovascular System; another etiology is significantly less likely
Not related	An AE is not related to the use of recombinant t-PA, anticoagulation medication, or the EkoSonic® Endovascular System; there is no temporal relationship or a much more likely alternative etiology exists

Unknown	An AE where the relationship to the use of recombinant t-PA, anticoagulation medication, or the EkoSonic® Endovascular System cannot be determined.
----------------	---

Outcome

The clinical course of all AEs should be followed until a medical outcome is determined (resolution, stabilization, or determination that it was unrelated to study participation). The clinical outcome of all AEs should be recorded as follows:

Death	Subject expired
Recovered	Subject returned to baseline health and functional status
Not yet recovered	Subject did not recover and symptoms or sequelae persist
Recovered with sequelae	Subject did recover but continues to experience clinical sequelae from the adverse event

Treatment or action taken

AEs and SAEs will be categorized by the actions taken in response to the event:

Intervention	Surgery or other invasive procedure
Non-surgical treatment	Drug initiation, interruption, dose reduction, dose increase, or discontinuation
None	No action was taken

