5.13 Expedited reporting of serious adverse events

Any AE that is considered serious must be reported to the device manufacturer, EKOS Corporation, within 24 hours of the site's knowledge of the event throughout the study via the e-mail address [REDACTED]

At the time of Sponsor notification, the Investigator shall enter into EDC as much of the information listed below as possible.

- a. Subjects demographics
- b. Pre-existing conditions
- c. The adverse event's description
- d. Date and time of AE onset
- e. Severity
- f. Treatment
- g. Results of diagnostic testing
- h. Duration of sequelae

- i. Outcome (if known)
- j. Information on suspected medications including dose, route of administration, frequency, dates, lot number, expiration date, and concomitant medications

When a SAE is reported, the device must be retained and returned to EKOS (see above for address for return devices). The EKOS representative may contact the Investigator to collect additional information on the EkoSonic® System.

When reporting a death, the primary event or condition that caused or contributed to the fatal outcome should be reported as the serious adverse event. Death would be reported as the outcome of the serious adverse event. If the cause of death is unknown at the time of reporting, report "unknown cause of death".

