5.14 Safety Monitor

A safety monitor shall review and adjudicate all SAEs and bleeding events during the study. The safety monitor will determine if the AE meets the definition of serious and unexpected and shall notify the sponsor if the number or type of events is of concern.

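### Section 5.3 item 2 defines a life-threatening event by what a worse version of it might have done, which conflicts with the rest of the protocol and can make SAE classification over-inclusive and inconsistent between sites.

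*Protocol*

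**What the plan says.** Section 5.3 opens by calling an adverse event serious if "in the view of either the investigator or sponsor, it results in any of the following outcomes", and then lists six items. Item 2 reads "Life-threatening (had the event occurred in a more severe form, might have caused death". Item 6 adds a further class: "Important medical events that may not result in death, be life-threatening, or require hospitalization may be considered serious when" medical judgment finds that they may jeopardize the subject.

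Seriousness then has consequences elsewhere in the protocol:

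- Section 5.13: "Any AE that is considered serious must be reported to the device manufacturer, EKOS Corporation, within 24 hours" of the site learning of it, and the device must be kept and returned.
- Section 5.8: all adverse events are recorded through Day 30. After that, only SAEs and events related to venous thromboembolism or the study treatment are collected.
- Section 5.14: "A safety monitor shall review and adjudicate all SAEs and bleeding events during the study", and "The safety monitor will determine if the AE meets the definition of serious and unexpected".
- Section 6.2.3: one of the three adverse event tables, table (c), is the SAE table.

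**The concern.** Item 2 does not ask whether this subject was in danger of dying. It asks whether some worse form of the same event could have killed. Many minor events have a potentially fatal severe form, so the test has no clear lower limit.

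Two things are at stake. First, events that put nobody at risk of death can be counted, expedited and followed as SAEs. Second, a site that applies the sentence literally and a site that applies the usual sense of the term will classify the same event differently. The study has a single arm, so no control group shares the distortion, and readers would take the SAE proportion at face value.

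**Working it through.** The protocol states no figure for this point and none can be derived. The check is to read item 2 against the other places that use or presuppose the same concept.

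1. **Lead-in of Section 5.3.** The event must itself lead to a listed outcome ("in the view of either the investigator or sponsor, it results in any of the following outcomes"). Items 1, 3, 4 and 5 fit that: each names something that happened. Item 2 names something that would have happened to a different, more severe event.

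2. **Item 6 of Section 5.3.** This item presupposes important events that are not life-threatening and makes their seriousness depend on medical judgment that the subject may be jeopardized. An event that may jeopardize a subject would usually be capable of killing in a more severe form, so item 2 as worded takes in most of that class and bypasses the judgment that item 6 requires.

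3. **Section 5.9.** The general principle there is that "major bleeds are those that result in death, are life-threatening, cause chronic sequelae or consume major health-care resources". If being life-threatening helps to mark a bleed as major, some bleeds are not life-threatening. Fatal bleeding is a listed form of bleeding in Sections 3.3 and 5.9, so under item 2 a small bleed can qualify because a larger one can kill.

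4. **Sections 5.10 and 5.14.** Section 5.10 requires recording through Day 365 of those bleeds that are serious. Section 5.14 names bleeding events alongside SAEs. Both wordings are needed only if some bleeds are not SAEs.

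5. **Section 5.12.** Severity has its own scale, starting at mild: "Awareness of a symptom or sign that does not interfere with the subject's usual activity". Item 2 brings severity, and a hypothetical severity at that, into the separate question of seriousness.

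An example shows the effect. Table 1 in Section 7.1 includes contrast reactions with no severity threshold. Take one graded mild under Section 5.12 that resolves without treatment. Under the lead-in and items 1 and 3 to 5 it is not serious. Under item 6 it is serious only if medical judgment says so. Under item 2 read literally it is serious, because a severe contrast reaction might cause death.

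Where the classification then matters:

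| Use of seriousness | Depends on item 2? |
|---|---|
| SAE table (c), Section 6.2.3 | Yes |
| 24-hour report and device return, Section 5.13 | Yes |
| Unrelated, non-bleeding events after Day 30, Section 5.8 | Yes |
| Bleeds after Day 30 | Little: Section 4.2.6 collects bleeding events at every follow-up visit |
| Safety monitor review of bleeds, Section 5.14 | No: all bleeds are reviewed |
| Major bleeding within 72 hours, pulmonary embolism, death, Section 6.2.3 | No: each is defined without Section 5.3 |

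**The case against.** The best defence is that classification is not automatic. It rests on the view of the investigator or sponsor, and a safety monitor then adjudicates. That limits the harm but does not remove the defect, because all of them are told to apply the same sentence: "The safety monitor will determine if the AE meets the definition of serious and unexpected". The monitor also receives only SAEs and bleeds. A non-bleeding event that one site does not call serious never reaches the monitor, so adjudication cannot fully even out differences between sites.

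Several other points stand. The error runs towards over-reporting, not towards missed events. No hypothesis test or numerical stopping rule in the protocol uses SAE counts. Bleeds, the most obvious example, are largely protected because they are reviewed and collected whether or not they are serious.

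A reader might infer that every bleed and most procedural events become serious and that the SAE table loses its meaning. The documents do not support that:

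- The judgment step in the lead-in remains, and no event rates are given.
- Several Table 1 entries carry their own threshold. Arrhythmia must need treatment, systemic infection must warrant antibiotics, and access-site bleeding and hematoma must be clinically significant. They are not examples of trivial events.
- Deaths, hospitalizations and permanent impairments still enter table (c) through other items. Events are tabulated by worst severity, so a mild event would show as mild, and tables of all events and of related events stand beside it.

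A reader might also try to size the effect by applying a guessed rate of minor bleeds to the 70 in Section 6.2.4. That number counts evaluable segments, whereas the SAE table uses the Safety Subject Set of Section 6.1. No rate in the documents supports such a figure.

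**Conclusion.** The point holds as a defect of definition. Item 2 sets a hypothetical test that its own section contradicts and that Sections 5.9, 5.10 and 5.14 do not assume. If sites follow it, SAE table (c), the 24-hour reports and device returns, and the post-Day-30 collection of unrelated, non-bleeding events can be over-inclusive and can differ across the up to 30 sites allowed in Section 4.0.

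The size cannot be computed from the documents. The efficacy endpoints and the major bleeding, pulmonary embolism and death analyses are untouched. The conclusion rests only on contradictions within the protocol, not on any outside definition. The practical effect assumes that at least some sites apply the sentence as written. It should be corrected, but it does not threaten the trial's main results.

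**What to change.** Replace the parenthesis in Section 5.3 item 2 with: *the subject was, in the view of the investigator or sponsor, at risk of death at the time of the event as it occurred; this does not include an event that might have caused death had it been more severe.* Leave items 1 and 3 to 6 unchanged, so that item 6 still captures events that jeopardize the subject.

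For SAEs already reported under item 2 alone, have the existing safety monitor re-adjudicate them against the new wording. Report the SAE count under both the old and the new wording. This matters because the study is single-arm and Section 6.2.5 shows that data had already been examined by November 2016. A change that lowers the SAE count after data were seen must be visible.

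The cost is a one-line amendment, a memo to the sites, the monitor's time on the affected events and one additional SAE count. No treatment, visit, endpoint or sample size changes.

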5.4 Unexpected

An AE is considered "unexpected" if it is not listed in the IFU or package insert or is not listed at the specificity or severity that has been observed; or, is not consistent with the risk information described in the general investigational plan or elsewhere in the current application, as amended.

5.5 Pre-existing medical conditions

A pre-existing medical condition is one that is present at the start of the study. Pre-existing medical conditions should be reassessed during the trial and reported as an AE only if the frequency, severity, or character of the conditions worsens significantly or unexpectedly during the study. When reporting such adverse events, the description should convey that the pre-existing condition has changed by including applicable descriptors (for example, "more frequent" headaches). Scheduled hospitalizations required for diagnostic or elective surgical procedures for the management of unchanged pre-existing medical condition should not be considered AEs.

5.6 Device Deficiency, Device Failures and Malfunctions

Manufacturers must report device-related deaths, serious injuries and malfunctions to the FDA whenever they become aware of information that reasonably suggests that the reportable event occurred (one of their devices has or may have caused or contributed to the event).

Definitions

A device failure is defined as the device is used in accordance with the IFU, but does not perform according to IFU and negatively impacts the treatment.

A device malfunction is defined as an unexpected change to the device that is contradictory to the IFU and may or may not affect device performance.

Reporting Requirements

All device failures and malfunctions will be documented on the electronic case report form (eCRF), reported to EKOS within one working day after the designated study site personnel first learn of the event, and reported to the IRB (if required) within the IRB required timeframe.

Device malfunction

In the event of a device malfunction the EKOS Customer Helpline [REDACTED] shall be contacted for assistance. If the device cannot be restarted or is damaged in some way, if possible, the malfunctioning device should be replaced to continue ultrasound treatment for the desired length of time. If it is not possible to replace the device, thrombolytic infusion can be continued without the activation of ultrasound. The malfunctioning device should be retained for return to EKOS. When the malfunction is reported to EKOS, product return information will be provided.

Return devices to the address below:

EKOS Corporation
[name]
[name]

Fax: [REDACTED]

Email: [REDACTED]

5.7 Documentation of adverse events

AEs shall be reported when noted during the hospitalization for the initial treatment and in the subject's medical record through the 30 day follow-up period. Subjects shall be encouraged to report AEs spontaneously or in response to non-directed questioning by their usual healthcare providers (for example, in response to the question "How has your health been since you last visit?"). If it is determined that an AE has occurred, the study staff member entering data into the eCRF should obtain all of the information necessary to complete the AE section.

5.8 Reporting and duration of AE reporting period

Because the EkoSonic® Endovascular System is a commercial medical device, Investigators will comply with any hospital user reporting requirements. All observed or reported AEs including type of event, severity and relationship to the procedure, device use, thrombolytic and anticoagulant drug use will be recorded in the eCRF during hospitalization and through

30 day follow-up. At subsequent visits, SAEs and AEs related to venous thromboembolism or the EkoSonic® treatment will be collected.

5.9 Adverse events related to alteplase and definition of major bleeding

AEs related to alteplase are well-described and consist mainly of bleeding complications, including major and intracranial hemorrhage. The incidence of these complications has been quantified in subjects receiving comparatively large systemic doses of alteplase for acute myocardial infarction, stroke, and acute pulmonary embolism. Any bleeding that is attributable to alteplase is most likely to occur within 24 hours of treatment and is very unlikely to occur after 72 hours. Therefore, all bleeding events that occur within 72 hours of ultrasound-accelerated catheter-directed fibrinolysis will be attributed to the use of alteplase.

The following definition of major bleeding¹² (ISTH) shall be used: As general principles, a definition of major bleeding needs to be based on objective criteria, and major bleeds are those that result in death, are life-threatening, cause chronic sequelae or consume major health-care resources. With this in mind, the Control of Anticoagulation Subcommittee recommends the following criteria for major bleeding in non-surgical subjects:

1. Fatal bleeding, and/or
2. Symptomatic bleeding in a critical area or organ, such as intracranial, intraspinal, intraocular, retroperitoneal, intra-articular or pericardial, or intramuscular with compartment syndrome, and/or
3. Bleeding causing a fall in hemoglobin level of 20 gL⁻¹ (1.24 mmol L⁻¹) or more, or leading to transfusion of two or more units of whole blood or red cells

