6.2.3 Safety Analysis

Safety analyses will be performed for the Safety Subject Set.

For the primary safety analysis, the number and percentage of subjects with major bleeding within 72 hours of initiation of EkoSonic® Treatment will be reported with a 95% Wilson confidence interval.

Secondarily, the frequencies and proportions of subjects with symptomatic PE (diagnosed using CTPA, SPECT VQ, etc.) during hospitalization for the study procedure, and death during the 365 day follow-up period will be reported with 95% confidence intervals.

In addition, adverse events experienced will be mapped to standard terms and summarized. For a given event, the frequency and proportion of subjects reporting it will be tabulated according to the worst severity experienced. Separate tables will be constructed for (a) all reported events, (b) events judged as related to the study procedure/device/medications, and (c) SAEs.

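### The relatedness grades in 5.12 leave out the study procedure, and 5.9 attributes early bleeds to alteplase by timing alone, so what enters table (b) of 6.2.3 is not settled

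*Protocol*

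**What the plan says.** Four parts of the protocol bear on which adverse events count as related.

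- **Section 5.9** sets a rule for bleeds by timing: "all bleeding events that occur within 72 hours of ultrasound-accelerated catheter-directed fibrinolysis will be attributed to the use of alteplase". Its rationale is that alteplase bleeding mostly comes early and is very unlikely after 72 hours.
- **Section 5.12** requires a relatedness grade for every AE and makes no exception for bleeds. Its lead sentence includes the procedure: "Each AE should be evaluated as to whether it was related to the study procedures, thrombolytic and anticoagulation drugs", and the device. The definitions beneath it are narrower. *Definite* reads: "An AE that has a causal relationship to the drug (recombinant t-PA), anticoagulation medication, or the EkoSonic® Endovascular System". *Probable*, *Not related* and *Unknown* name the same three causes. *Not related* applies when "there is no temporal relationship or a much more likely alternative etiology exists".
- **Section 5.8** lists four relationships to collect: "relationship to the procedure, device use, thrombolytic and anticoagulant drug use will be recorded in the eCRF".
- **Section 6.2.3** plans three AE tables. Table (b) holds "events judged as related to the study procedure/device/medications"; table (a) holds all events and table (c) holds SAEs.

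Section 5.14 has a safety monitor review and adjudicate all SAEs and all bleeding events. The determination it names is this: "The safety monitor will determine if the AE meets the definition of serious and unexpected".

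**The concern.** Table (b) is a planned safety output of a study whose primary objective (section 3.1) includes safety. Two features of the text leave its content open.

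First, the grading scale does not cover one of the causes that the table is meant to show. Section 7.1 names vessel injury from catheter placement as the expected risk and lists access-site bleeding among anticipated events, so procedural harm is not a remote case.

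Second, for bleeds there are two routes to a causal label: timing alone in 5.9, and case-by-case grading in 5.12. Nothing ranks them. The timing rule also has no stated clock.

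At stake is whether a given event appears as related in one descriptive table. Sites grade events with the protocol's definitions, so a procedural cause recorded as *Not related* could not be recovered later by a programming rule alone.

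**Working it through.** The protocol states no figure on this point, so there is none to reproduce. The check sets the sections side by side and adds one piece of window arithmetic.

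**Step 1. Causes named in each place**

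| Place | Procedure | Device | Alteplase | Anticoagulant |
|---|---|---|---|---|
| 5.8, eCRF recording | yes | yes | yes | yes |
| 5.12, lead sentence | yes | yes | yes | yes |
| 5.12, all four grade definitions | **no** | yes | yes | yes |
| 6.2.3, table (b) | yes | yes | yes (medications) | yes (medications) |
| 5.9, bleeds within 72 h | – | – | yes, by timing | – |

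Only the definitions omit the procedure. Section 2.2 describes the EkoSonic system as the single-use device (IDDC and MSD) plus the control system. The guidewires, sheaths and angioplasty balloons of section 4.2.3 are not part of it.

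**Step 2. An event caused only by the procedure**

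Take a guidewire perforation before the IDDC is placed.

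- Section 4.2.3: the procedure is abandoned and the subject is failure-to-cross, so no study alteplase is infused.
- Section 6.1: venous access was attempted, so the subject is in the Safety Subject Set.
- Section 5.9: there was no fibrinolysis, so the timing rule does not apply.
- Section 5.12 definitions: alteplase and the EkoSonic system are not causes. If the investigator also judges enoxaparin not to be a cause, the event meets the wording of *Not related*.
- Section 6.2.3: the event is then absent from table (b), although that table is meant to include procedure-related events.

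Under the 5.12 lead sentence the same event is related and present.

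**Step 3. A bleed inside the 5.9 window in a subject who received alteplase**

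| 5.12 grade | In table (b) by 5.12 | In table (b) by 5.9 |
|---|---|---|
| Definite or Probable | yes | yes |
| Not related | no | yes |
| Unknown | not stated | yes |

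The rules diverge only in the last two rows. Section 5.2 leans towards case-level judgement, since a reasonable possibility of causation there means that "there is evidence to suggest a causal relationship between the intervention and the AE". So does the word judged in table (b). Neither says what happens to a bleed covered by 5.9.

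**Step 4. The clock in 5.9**

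Let L be the infusion length, planned at 12 to 48 h (section 4.2.3), and count hours from infusion start.

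- From infusion start, the window closes at hour 72.
- From infusion end, it closes at 72 + L: 72 + 12 = 84 h to 72 + 48 = 120 h.
- The difference is L, so 12 to 48 h as planned, and less if an infusion stops before its planned minimum.
- From venous access, which section 4.0 defines as initiation and which anchors the bleeding endpoint in 3.3, the window closes before hour 72 by the access-to-infusion interval. The protocol does not give that interval.

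**Step 5. Outputs that depend on relatedness**

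The primary safety analysis counts major bleeds within 72 hours of initiation whatever their cause. Tables (a) and (c) do not select on relatedness, and neither primary efficacy criterion uses AE data. Only table (b) is affected.

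**The case against.** The strongest reply is that the sections can be read together. Section 5.9 is a specific, conservative presumption for one event type and one drug; section 5.12 is the general scale for everything else. On that reading a bleed in the window is alteplase-related by rule and its other causes are still graded. This is reasonable, and it means that a flat contradiction between 5.9 and 5.12, which a reader might infer, is more than the text supports. What stands is that the protocol does not state this precedence.

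Other replies also limit the point.

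- A reader might infer that a procedural event has no way of being called related. That goes too far: 5.8, the 5.12 lead sentence and table (b) all name the procedure, and an investigator may follow them. The definitions look like a drafting omission.
- A reader might treat procedural bleeds as automatically *Not related*. They are not. Subjects are to be on enoxaparin for at least 48 hours beforehand (4.2.2, 4.3), anticoagulation is in every definition, and *Not related* needs a much more likely alternative cause or no temporal relationship. That is a judgement, so the example in Step 2 carries its condition explicitly.
- A reader might infer that bleeds go without central review. Section 5.14 says otherwise. Relatedness is simply not among the determinations it names.
- The clock in 5.9 could be taken from 3.3 and 4.0, since 5.9 carries the same major-bleeding definition. That is a natural reading, but not a stated one.
- Whether *Unknown* counts as related can properly be left to the SAP.

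**Conclusion.** There is an internal inconsistency, minor in effect and confined to table (b) of 6.2.3. The grade definitions in 5.12 omit a cause that three other places in the protocol name, so applying them literally can remove a procedure-only event from the table meant to show it. Separately, 5.9 and 5.12 give two routes to a causal label for early bleeds without ranking them, and the 72 hours in 5.9 lack a time zero.

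The number of events affected is unknown and may be zero. No percentage can be given: the protocol contains no bleed counts, and the 70 in the power section is a number of evaluable segments, not the size of the Safety Subject Set. A reader might infer that the major-bleeding result is in doubt; it is not, because it ignores cause and has its own anchor.

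The conclusion assumes that sites grade from the definitions as printed and that no eCRF instruction outside the protocol already supplies the missing cause.

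**What to change.** 1. Add the study procedure to the *Definite*, *Probable*, *Not related* and *Unknown* definitions in 5.12, so that they match the lead sentence, 5.8 and 6.2.3.
2. State in 6.2.3 that table (b) is filled from the 5.12 grade, given separately for procedure, device, alteplase and anticoagulant. Section 5.8 already calls for these four relationships.
3. Keep the 5.9 attribution as a separately reported flag with a stated time zero, and show how many bleeds are related by the flag alone.
4. Leave the major-bleeding endpoint in 3.3 and 6.2.3 as it is.

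The cost is text in three sections, settled before table (b) is built and without sight of its counts. AEs already graded *Not related* or *Unknown* need one re-read for procedural cause. The time of the start of infusion is already needed for the time-to-discharge endpoint in 3.2.1, and the time of venous access for the bleeding endpoint; an infusion-end clock would also need the stop time.

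The effect on the count can go either way. Adding the procedure may raise the number of related events. Showing the 5.9 attribution as a flag beside table (b) may leave the table's own count lower than if 5.9 were applied to it, which is why the flag-only bleeds must be reported.
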